3.3 Power and Sample Size (as was written in the grant)

Power Analyses and Sample Size Calculations for Delirium (Aim 1). Based on data collected during our BRAIN-ICU Study, we anticipate that patients in the control (placebo) group in MIND-USA will have a mean ± SD of 6.8±5.2 delirium/coma-free days during the 14-day Treatment Period. At a 2-sided significance level of 2.50%, after Bonferroni adjustment for 2 pairwise comparisons (each active treatment will be compared to placebo), a trial of 187 patients per treatment group (total N=561) will have 92% analytical power to detect a 2-day improvement in delirium/coma-free days. Importantly, this sample size will also provide 80% power to detect a 2.5-day improvement in DCFDs within 4 subgroups expected to be ~45% (N=252) of the study population: severe sepsis, age ≥65 years, high illness severity (APACHE II ≥25), and medical vs. surgical patients. We will also conduct a hypothesis-generating subgroup analysis for patients enrolled with preexisting cognitive impairment (~25% of study population, N=140).

Power Analyses for Mortality and ICU LOS (Aims 2 and 3). Assuming 40% one-year mortality in the control (placebo) group, this study will have 80% power to detect a 13% absolute difference in one-year mortality at a 2-sided significance level of 1.67% (if control mortality is 50%, study has 80% power to detect 14% difference). For ICU length of stay (LOS), this study will have 80% power to detect a 2-day (24%) difference at a 2-sided significance level of 1.67% assuming an 8.2±7.6 day ICU LOS in controls.

Timing of Final Analysis

In-Hospital Database Cleaning & Lock Procedures

MIND-USA uses the REDCap electronic data capture platform for data collection. Upon completion of the in-hospital portion of the MIND-USA study, the following procedures will be followed and documented within the Database Cleaning & Lock SOP:

- 1. VCC will work with site coordinators to address all data issues revealed by ongoing data cleaning. This process will continue until all issues have been addressed.
- Upon completion of in-hospital data cleaning, the REDCap database MIND-USA Study: Exclusion Log will be locked in the following way:
 - a. Initially all users with current "view and edit" user privileges will be moved to "read only" user privileges.
 - b. After the window closes for sites to export their data the database will be permanently moved to inactive status (meaning that no data can be changed).

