
Severity of Illness

Due to the nature of clinical data collection, we have some missing values for APACHE II and SOFA components despite our coordinators' best efforts. We handled these missing values in the following ways:

APACHE II (ICU admission only)

- Oxygenation: If no arterial blood gas was done, we converted the lowest O2 saturation
 to PaO2 per the EPIC II conversions and assigned points based on PaO2 alone. O2
 saturations below the lowest level included in the conversion table were assigned the
 lowest PaO2; O2 saturations of 100 were assigned the highest PaO2.
- pH: If no arterial blood gas was done, we used the serum HCO3 conversions noted in the original reference.
- Glasgow Coma Score: If no GCS was available, we assigned points for the APACHE
 using the lowest RASS on the day of ICU admission using Vasilevskis et al's point
 values for the SOFA.
- All other components: If no values were available on a given day, we looked for a value on the closest day within the three full days after ICU admission. If none was available, we assumed that no measurement implied no clinical reason to suspect dysfunction, and assigned a normal value (0 points).

SOFA (ICU admission + daily throughout intervention period)

- Substitutions for specific components:
 - Respiratory: If P/F ratio was not available, we used the lowest S/F ratio, per Pandharipande et al.
 - Central nervous system: If no GCS was available, we used the lowest RASS available that day, per Vasilevskis et al, method C.
- Missing data at ICU admission: Using only data from ICU admission, there are 28 consented patients and 7 randomized patients missing at least one SOFA component score. For these patients' missing components, we imputed the next available value within the following two calendar days. If none was available, we assumed a normal value (0 points). (This could happen either because there was no clinical reason to order labs, or because the patient was not consented within three days of ICU admission and thus no study data was collected in that period.)
- Missing data during the intervention period:
 - We were unable to calculate SOFA scores using raw data on 3 patient-days during the study period (randomization + 13 days). (Missingness is much higher after the official intervention/post-intervention periods, when patients were no longer being actively followed for daily data collection.)

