Patients could have multiple assessments on a given study day. On a given day, a patient was considered delirious if any assessment was considered delirious; comatose if no assessments met criteria for delirium and at least one was considered comatose; and normal if no assessments met criteria for delirium or coma, and at least one was considered normal.

Handling Missing Data

Prior to unblinding, the data shows that among all consented patients, 401 (4%) in-hospital patient-days have insufficient information to determine mental status (due to missing data or study withdrawal). Among randomized patients during the intervention period, 251 (4%) of patient-days have missing mental status, again due either to missing data or study withdrawal. Mental status can change quickly; therefore, simple imputation methods like last observation carried forward could be inaccurate. Since we have strong covariate data, we performed single imputation using polytomous logistic regression, including the following variables as covariates in the imputation.

- Baseline: age at consent; gender; BMI; education; level of proficiency in English; insurance; home antipsychotic use; Charlson comorbidities index; CSHA Clinical Frailty Score; APACHE II Acute Physiology Score
- Daily:
 - Medications (clonazepam, dexmedetomidine, propofol, remifentanil, antipsychotics, benzodiazepines, opioids [IV and PO], antibiotics, anxiolytics, statins)
 - Variables indicating severity of illness (CV SOFA, creatinine, urine output, platelets, lowest recorded RASS, Glasgow Coma Scale, P/F ratio, S/F ratio, bilirubin)
 - Any mental status data available the day of, the day before, and the day after the missing day

All summary variables (delirium/coma-free days, delirium duration, and coma duration) are presented using imputed mental status.

9. Software Details

R version 3.4.4 (2018-03-15) or above will be used for all analyses. Versions of specific packages used for analysis will be noted in the analysis report. The checkpoint.package will be used to preserve R package versions throughout the manuscript submission and review process.

10. References

- 2. R. Gray. A class of k-sample tests for comparing the cumulative incidence of a competing risk. Ann Stat, 16:1141-1154, 1988.

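### When GCS is missing, the SAP fills the APACHE II coma item with RASS-derived SOFA points and states no conversion to the APACHE II scale

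*SAP*

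**What the plan says.** SAP section 8, Severity of Illness, gives the rules under "APACHE II (ICU admission only"). For the coma item: "If no GCS was available, we assigned points for the APACHE" "using the lowest RASS on the day of ICU admission", with the points taken from a cited study's "values for the SOFA". By its title in the SAP reference list, that study validates a modified SOFA that uses RASS.

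The neighbouring rules work differently. For oxygenation without a blood gas, saturation is first converted to PaO2 and points are then assigned. For pH, the bicarbonate conversion comes from the instrument's own source paper. For the SOFA CNS component, the same RASS study is used, on the SOFA's own scale.

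APACHE II appears elsewhere as follows:
- Protocol 1.0 (Specific Aims), Protocol 11.1 and SAP 3.3 name a subgroup with "high illness severity (APACHE II ≥25").
- The mental-status imputation model in SAP section 8 has the "APACHE II Acute Physiology Score" among its baseline covariates.
- SAP section 5 promises a description of severity of illness at ICU admission, without naming the score.

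**The concern.** Points from one instrument are entered in another. If the SOFA consciousness item has a shorter range than the APACHE II item, every deeply unresponsive patient without a GCS gets too low an APACHE II. The error runs in one direction and grows with depth of coma. Protocol 6.1 expects patients often to be comatose or delirious early in their illness, so such patients will not be rare.

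Three uses are at stake: how sick the cohort looks at baseline, who counts as APACHE II ≥25 if that subgroup is analysed, and one covariate in the model that fills missing days of the primary outcome.

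**Working it through.** **Inputs from the documents.** SAP 3.3: DCFD SD 5.2; two-sided alpha 0.025; 187 per arm (561 in total) for a 2-day difference; subgroups of about 45% (N=252) for 2.5 days. SAP section 8: 251 patient-days (4%) with missing mental status among randomized patients in the intervention period.

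**Assumptions (not printed in the documents).** APACHE II coma item = 15 − GCS, range 0 to 12. SOFA CNS item = 0, 1, 2, 3, 4 for GCS 15, 13-14, 10-12, 6-9, 3-5. The RASS-derived SOFA points equal those the patient's GCS would have given. The Acute Physiology Score includes the coma item.

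**Step 1. The plan's power figures.** Power = Φ(δ / (σ√(2/n)) − z), with z = 2.241 for alpha 0.025.
- Overall: 2 / (5.2 × √(2/187)) = 3.719; 3.719 − 2.241 = 1.478; power 93.0% (stated 92%).
- Subgroup: 252 / 3 = 84 per arm; 2.5 / (5.2 × √(2/84)) = 3.116; 3.116 − 2.241 = 0.874 before rounding; power 80.9% (stated 80%).

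Both reproduce to within about a point. The issue is not a wrong power figure.

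**Step 2. Shortfall from the substitution.** Shortfall = (15 − GCS) − SOFA CNS points.

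| GCS | APACHE II item | SOFA CNS | Shortfall |
|---|---|---|---|
| 15 | 0 | 0 | 0 |
| 14 | 1 | 1 | 0 |
| 13 | 2 | 1 | 1 |
| 12 | 3 | 2 | 1 |
| 11 | 4 | 2 | 2 |
| 10 | 5 | 2 | 3 |
| 9 | 6 | 3 | 3 |
| 8 | 7 | 3 | 4 |
| 7 | 8 | 3 | 5 |
| 6 | 9 | 3 | 6 |
| 5 | 10 | 4 | 6 |
| 4 | 11 | 4 | 7 |
| 3 | 12 | 4 | 8 |

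The shortfall is never negative, so under these assumptions scores can only be too low.

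**Step 3. The cut-off of 25.** At GCS 8 (shortfall 4), a true total of 25 to 28 is scored 21 to 24. At GCS 3 (shortfall 8), a true total of 25 to 32 is scored 17 to 24.

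**Step 4. Power if the ≥25 subgroup is analysed.** The share of the subgroup lost is unknown, so take 5%, 10% and 20% as an assumed range. Per-arm n becomes 79.8, 75.6 and 67.2, and power for 2.5 days becomes 78.7%, 76.3% and 70.7%.

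**Step 5. Where the score is and is not used.** The adjusted models (SAP section 7, Covariates) take SOFA at randomization without its CNS part, plus RASS; APACHE II is not a covariate. The effect-modification list in SAP section 7 has age, severe sepsis, IQCODE, and medical versus surgical; APACHE II is absent. The Acute Physiology Score does enter the imputation model, which also holds daily lowest RASS, daily GCS, and any available mental status from the same and adjacent days.

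**The case against.** The strongest case against is that little depends on the score.

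- **Cut-off.** No analysis listed in SAP section 7 uses APACHE II ≥25. In the SAP the cut-off appears only in section 3.3, whose heading marks it as grant text. This stands. A reader might infer that a planned SAP subgroup analysis is corrupted; the documents do not support that. The consequence is tied to the subgroup the protocol promises, and its absence from the SAP list is a separate inconsistency.
- **Primary outcome.** A reader might infer bias in the DCFD comparison. The documents do not support that either. The imputation fills 4% of patient-days, direct measures of consciousness are in the same model, and the score is fixed on the ICU admission day, so nothing suggests an error that differs by arm.
- **Size.** A reader might take 8 points as typical. It is the extreme, reached only at GCS 3 and only under scales the documents do not print. A misclassification rate would also need the APACHE II spread and the share without a GCS, and neither is given. SAP section 8 counts 7 randomized patients missing any SOFA component at admission, which is not a count of missing GCS.
- **Loose wording.** The authors may have meant RASS to GCS, then APACHE points. The text does not say so, and a programmer following it would enter SOFA points.
- **Sedation.** The lowest RASS under sedatives could give near-maximal coma points. This is a fair limit on precision, but it does not defeat the change, because the SAP already uses the day's lowest RASS in the same way for the SOFA CNS component.

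**Conclusion.** The point holds as a scoring error in a stated rule. As written, the APACHE II coma item receives SOFA-scale points when GCS is missing, whereas the adjacent oxygenation and pH rules use conversions suited to APACHE II.

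Under the assumed standard scales, the under-scoring is 0 at GCS 14-15, 1 to 3 points at GCS 9-13, and 4 to 8 points at GCS 3-8. The number of patients affected is unknown. The clearest effect is on the baseline severity description. The ≥25 subgroup is affected only if it is analysed, and the effect through the imputation covariate is probably slight. The adjusted treatment models do not use APACHE II directly.

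**What to change.** Rewrite the coma-item rule in SAP section 8. When GCS is missing, map the lowest admission-day RASS to a GCS value (for example, the midpoint of the GCS band that matches the RASS-derived SOFA CNS score), then assign 15 minus that GCS as the APACHE II points. Recompute APACHE II and its Acute Physiology Score before they go into the baseline table, the imputation model and any ≥25 subgroup.

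Report how many randomized patients had the item filled this way, and note that RASS under sedation makes the mapped GCS approximate. State whether APACHE II ≥25 remains a planned subgroup. If the authors already convert RASS to GCS in their code, the text should say so.

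The cost is a few sentences in the SAP and one recode of data already held. The recode needs only ICU-admission data, so it can be done without knowledge of treatment arm.

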Time to Event Outcomes

We will use Cox proportional hazards regression for mortality. For all other time to event outcomes (ICU and hospital discharge, ICU readmission, and liberation from mechanical ventilation), we use Fine-Gray competing risks regression, treating death as our competing risk. (For ICU readmission and liberation from mechanical ventilation, hospital discharge without experiencing the outcome will be treated as an additional competing risk.) Patients who withdrew in the hospital with no discharge or death information available will be censored at the time of withdrawal; we will censor at x.01 days anyone who has experienced neither death nor the outcome of interest by x days, where x is the end of the time frame specified above for each outcome. Details on censoring will be provided with each analysis.

"Time 0" will be the time of randomization for each of these outcomes, with the exception of ICU readmission; for this outcome, "time 0" will be the time of the first ICU discharge, and only patients who survived their first ICU admission will be included.

Long-Term Outcomes

We will use the same modeling techniques as described in "Unadjusted Analyses" above; however, here, we will adjust for the covariates listed below.

Model Assumptions

Model assumptions will be evaluated graphically. Proportional odds assumptions will be checked using logistic regression with multiple cutoffs for proportional odds assumption (see Harrell's *Regression Modeling Strategies*, section 13.3.3) and Schoenfeld residuals will be used for proportional hazards. If linear regression is used for long-term outcomes, we check residual vs fitted plots and quantile-quantile plots to ensure assumptions are met. For negative binomial models, we will check goodness-of-fit measures.

Covariates

Covariates for all multivariable regression models include (all demographic or ICU admission characteristics):

- Age at study consent
- Preexisting CI, via the IQCODE (performed via patient or surrogate questionnaire)
- Preexisting frailty, via the CSHA Clinical Frailty Score
- Preexisting comorbidities, via the Charlson Comorbidities Index
- SOFA on the day of randomization, excluding the CNS component
- Level of arousal at randomization, via the RASS closest to the time of randomization

Prior to modeling, we perform redundancy analyses to ensure that no covariates completely explain any of the others (resulting in multicollinearity).

Exploratory Analysis

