- o If the data required to calculate a given component was unavailable, we imputed the closest non-missing component score before *or* after the missing day, up to two full days away (missing day +/-2 days). If data was available X days both before *and* after the missing day, we prioritized past over future values.
- If, after this imputation, values are still missing, we assume that no available data indicates no clinical reason to suspect organ dysfunction and therefore impute a normal value for that component. Again, this applies to 3 patient-days during the study period.

Medications

- Benzodiazepines include midazolam, lorazepam, and/or diazepam. Doses are expressed in midazolam equivalents.
- Opioids include fentanyl, morphine, and/or hydromorphone. Doses are expressed in fentanyl equivalents.
- Antipsychotics include open-label haloperidol, open-label ziprasidone, quetiapine, aripiprazole, olanzapine (including in combination with fluoxetine), and/or risperidone.
 Doses are expressed in haloperidol equivalents.
- All conversion formulas can be found in this spreadsheet.

Mechanical Ventilation

During the course of the study, patients could be on invasive mechanical ventilation (MV), noninvasive positive pressure support (NIPPV), both, or neither. For our purposes, "time on MV" describes the number of days each patient was on *either* type of MV beginning at the time of randomization, including time between discontinuation of MV and reinitiation or death, if that time is less than 48 hours. (In other words, if a patient was extubated at 12pm and died at 3pm, those final three hours are included in the total time on MV.)

"Liberation from mechanical ventilation" indicates the first discontinuation of either type of MV which was followed by at least 48 hours alive without reinitiation of MV.

Delirium/Coma-Free Days

This primary outcome variable is calculated over the 14 days including and immediately following randomization. It is defined as days alive and without brain dysfunction.

Mental Status (Delirium and Coma)

Determining Mental Status Using CAM and RASS

We determined mental status for a given assessment using the following criteria:

- 1. Comatose: RASS -4 or -5, or RASS missing and CAM Unable to Assess
- 2. Delirious: RASS missing or >= -3, and CAM Positive

3. Normal: RASS missing or >= -3, and CAM Negative

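### The model that fills missing delirium/coma days has no treatment-arm term, so a real arm difference is slightly attenuated: between near 0 and about 4% of the effect

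*SAP*

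**What the plan says.** SAP section 8 (Definitions and Derived Variables), under Mental Status, Handling Missing Data, describes the imputation: "we performed single imputation using polytomous logistic regression, including the following variables as covariates in the imputation".

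- **Baseline terms:** "Baseline: age at consent; gender; BMI; education; level of proficiency in English; insurance; home antipsychotic use; Charlson comorbidities index; CSHA Clinical Frailty Score", and then the APACHE II acute physiology score.
- **Daily terms:** sedatives, opioids, antipsychotics and other drugs; severity measures that include "platelets, lowest recorded RASS, Glasgow Coma Scale"; and "Any mental status data available the day of, the day before, and the day after the missing day".

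Treatment arm is on neither list. The Medications paragraph of the same section shows that the antipsychotic term does not carry the assignment: "Antipsychotics include open-label haloperidol, open-label ziprasidone, quetiapine" and other named agents, with no mention of blinded study drug.

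On the amount missing among randomised patients in the intervention period, the SAP reports that "251 (4%) of patient-days have missing mental status, again due either to missing data or study withdrawal". It splits this figure neither by cause nor by arm. Section 8 also says that delirium/coma-free days, delirium duration and coma duration all use the imputed status.

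SAP section 7 makes the adjusted analyses primary. Their covariates include IQCODE and "Level of arousal at randomization, via the RASS closest to the time of randomization", neither of which is in the imputation list.

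**The concern.** Leaving arm out of an imputation model assumes that, once the listed variables are known, the missing status does not depend on arm. If a drug helps or harms, that holds only where the listed variables carry the whole effect. Elsewhere, days in all three arms are filled from one common relation, and the imputed part of the endpoint shows less contrast than the observed part.

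Benefit and harm are diluted alike. SAP section 4 says that reporting will stress effect sizes and confidence intervals, and protocol section 2.8 expects the result to shape practice whether positive or negative. An avoidable pull toward no difference, however small, is an easy criticism of a neutral result.

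The point concerns the content of the imputation model. Whether imputation should be single or multiple is a separate question.

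**Working it through.** **Inputs.** From SAP section 3.3: control SD 5.2 days, 187 per arm (561 in total), difference 2 days, two-sided alpha 0.025, stated power 92%. From SAP section 8: 251 missing patient-days, given as 4%.

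**1. The plan's own figure.** Power = Φ(δ / (σ√(2/n)) − z), with z = 2.241 for two-sided 0.025. The standard error is 5.2 × √(2/187) = 0.538, so 2 / 0.538 = 3.719 and Φ(3.719 − 2.241) = Φ(1.478) = 93.0%. A noncentral t calculation gives 92.9%, and the Wilcoxon efficiency factor 3/π gives 91.8%. The stated 92% reproduces.

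**2. Share missing.** 251 / 561 = 0.45 day per patient. Over 561 × 14 = 7,854 days that is 3.2%. The SAP's 4% corresponds to 251 / 0.04 = 6,275 days, or 5,578 to 7,171 days over the rounding range 4.5% to 3.5%. The denominator was therefore not 7,854, and the SAP does not say what it was. I use 4% and show 3.2% to 4.5%.

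**3. Ceiling on the loss.** Suppose that imputed days carry no arm contrast at all, that the missing share m is equal across arms, and that the effect is spread evenly over days. Then observed difference = true difference × (1 − m). For m = 4%: 2 × 0.96 = 1.92 days, and Φ(1.92 / 0.538 − 2.241) = 90.8%.

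| Missing share | Observed difference (true 2 days) | Power |
|---|---|---|
| 0 | 2.00 | 93.0% |
| 3.2% | 1.94 | 91.3% |
| 3.5% | 1.93 | 91.1% |
| 4.0% | 1.92 | 90.8% |
| 4.5% | 1.91 | 90.5% |

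**4. How close to the ceiling.** This depends on what is observed around a missing day. An illustrative simulation used a two-state daily chain with differences between patients, placebo mean 6.7 and SD 5.3 days, a true difference of 2.08 days and 4% of days missing. With no arm term, attenuation was:

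| Pattern of missing days | Without neighbouring-day status | With neighbouring-day status |
|---|---|---|
| Scattered single days | 3.9% | 0.4% |
| Runs after withdrawal | 4.0% | 3.6% |

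With an arm term and scattered days, or with an arm term and runs but no neighbouring-day status, the full difference was recovered to within about 0.1%. The arm-term run for withdrawal with neighbouring-day status fell back on pooled day averages for sparse cells, so it is not relied on. With no true effect, the arm difference stayed at zero to within 0.01 day. This is an assumed model, not trial data, and it omits daily RASS, Glasgow Coma Scale and medications, which could lower the loss further.

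**The case against.** The strongest reply is that the draws are conditional. Each missing day is predicted from the patient's own status on that day and the days either side, and from RASS, Glasgow Coma Scale, medications and organ function. Where these are observed they carry part of any arm effect, which is why scattered gaps lose almost nothing.

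A reader might infer that days after withdrawal are simply filled with the three-arm average. The documents do not support that:

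- The first missing day normally has an observed day before it.
- Protocol section 10.0 allows record access after withdrawal unless authorisation is revoked, and the protocol's missing-data paragraph (section 11) plans observational follow-up, so daily data may exist for some of these patients.
- Even with no daily data, the baseline terms still condition the draw.

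The protection is nevertheless thin deep into a run of missing days.

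A reader might also infer that omitting IQCODE and randomisation RASS pulls the effect toward zero. Both are baseline variables, balanced in expectation by randomisation. Leaving them out weakens agreement with the adjusted model but does not by itself shrink the arm contrast, and the daily lowest RASS is already included.

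Finally, an arm-free model fitted before unblinding protects the blind. A masked arm code fitted to primary-outcome data would show masked between-arm differences to whoever fits it. That is a reason to choose who runs the model and when; it is not a reason to leave arm out for good.

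**Conclusion.** The point holds in a limited form. Arm is absent from the imputation list, nothing listed stands in for it, and the primary endpoint uses the imputed days. Under missing at random, a true difference is attenuated by between near 0 and about 4%: at most 0.08 of a 2-day difference, with power about 90.8% instead of 93.0%.

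The 4% ceiling assumes an equal missing share across arms and an effect spread evenly over days. Its power figure treats the endpoint as a comparison of means, as the sample-size calculation appears to do, whereas the primary analysis is a proportional odds model. Because the SAP does not split the 251 days by cause or arm, the documents cannot place the loss within this range.

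A reader might infer a fixed bias toward the null in all circumstances, or a threat to the trial's error rate. Neither follows. With no true effect and data missing at random there is no shift, so this route does not create a false positive. If missingness is informative and differs by arm, the direction is not fixed. This is a worthwhile refinement, not a defect that would change the trial's conclusion on its own.

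**What to change.** Add treatment arm, IQCODE and randomisation RASS to the existing imputation model. Do this in one of two ways: with a masked arm code, run by someone outside the blinded analysis team, or after database lock and unblinding. Report the missing patient-days by arm and by cause (withdrawal or missed assessment).

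Section 8 describes the imputation as already performed. If that data set is fixed as primary, keep it and prespecify the arm-inclusive imputation as a sensitivity analysis.

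The cost is one re-run of existing code and a small table. The one downside is that, before unblinding, whoever fits the masked code sees masked between-arm outcome differences. Running it outside the blinded team, or after unblinding, deals with that.
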